3.2.2 Treatment Exposure and Dose Intensity

To understand the general tolerability of ASLAN003, and the impact of interruptions and dose reductions, summaries of treatment exposure and dose intensity will be produced. For the purpose of this study, the term *exposure* relates to the number of days of treatment received (regardless of dose reductions), whereas *dose intensity*

relates to the proportion of intended dose received, taking account of interruptions and reductions.

For all patients, exposure to ASLAN003 will be calculated. To assess treatment exposure, the following will be calculated:

Intended Exposure to study treatment (days)

- Intended Exposure = last dose date – first dose date + 1

Actual Exposure to study treatment (days)

- Actual exposure = Intended exposure – total duration of dose interruptions

where the intended exposure is calculated as defined above, and dose interruptions include all days in which the patient receive no study medication, regardless of whether the interruption was intentional, or whether the patient forgot to take a dose.

Two measures of dose intensity will be calculated:

1. Percentage of Intended Dose (PID) – defined as the percentage of the actual dose delivered relative to the intended dose, *until treatment failure (for non-responders for OCRR) or relapse (for responders for OCRR)*.
2. Relative dose intensity (RDI) – defined as the percentage of the *actual* dose intensity delivered, relative to the *intended* dose intensity, *until the earlier of treatment discontinuation, treatment failure (for non-responders for OCRR) or relapse (for responders for OCRR)* (as defined by IWG and based on the site assessments).

The key difference between the two measures outlined above is that the former is based on the intended treatment plan of treatment until relapse (if responding) else for 4 cycles when treatment failure would be declared, and the latter takes account of treatment discontinuations prior to relapse/treatment failure (e.g. discontinuation due to toxicity), and calculates the dose intensity during the actual dosing period.

For the purpose of calculating both measures of dose intensity, the intended dose will be evaluated taking account of the patient's response status for OCRR. I.e. A responder will be a patient classified as having a best response of CR or CRi (Section 3.1.1) and a non-responder will be all other patients (including those with a best response of PR). Therefore:

- For patients with a best response of CR or CRi, in the event that the investigator does not discontinue study treatment relapse, any dosing information beyond treatment relapse will not be taken into account when calculating either measure of dose intensity.
- For patients with a best response of PR, any dosing data collected after the first 4 cycles will not be taken into account when assessing dose intensity
- For patients with a best response of treatment failure, in the event that the investigator does not discontinue study treatment after the protocol-defined window for treatment failure (4 cycles), any dosing information beyond treatment failure (the end of 4 cycles) will not be taken into account when calculating either measure of dose intensity.

Definitions of treatment failure and relapse can be found in Sections 3.1.1 and 3.1.2.

PID and RDI will be defined as follows:

PID = $100\% * d/D$, where d is the actual cumulative dose delivered up to treatment failure/relapse (or a censoring event) and D is the intended cumulative dose up to progression (or a censoring event). D is the total dose that would be delivered, if there were no modification to dose or schedule.

RDI = $100\% * d/D$, where d is the actual cumulative dose delivered up to the earlier of progression (or a censoring event) or the actual last day of dosing and D is the intended cumulative dose up to the earlier of progression (or a censoring event) or the actual last day of dosing.

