----------------------	--

	
18-24 AML patients ineligible for standard treatment (Part 1)
 
 ASLAN003 100mg QD[◇] 6 patients (completed) ASLAN003 200mg QD[◇] 6 patients ASLAN003 100mg BID[◇] 6 patients ASLAN003 200mg BID[△] 6 patients 
Expansion cohort* 20 patients (Part 2)
 
◇ If showing clinical benefit in the patient, ASLAN003 will be continued until disease progression, development of unacceptable toxic effects, or withdrawal of consent. △ An additional cohort of 6 patients in ASLAN003 200mg BID may commence once steering committee review all safety data in ASLAN100mg BID cohort showing tolerability signals. * An expansion cohort of 20 patients will be recruited to study the optimum dose selected by the steering committee.
 
Abbreviations: AML = acute myeloid leukemia; QD = once daily, BID = twice daily.

Number of patients:
	
Up to a total of 18-24 patients are planned to be enrolled in Part 1 of this Phase IIA study to be conducted in Australia, Singapore and other countries.
 
Approximately 20 patients are planned to be enrolled in the expansion cohort of Part 2 of this Phase IIA study to be conducted in Australia, Singapore and other countries.

Study Population:
	
Inclusion Criteria
 
Patients who meet all of the following criteria are eligible for enrollment in the study:
 
 1. Patients who are of or older than the legal age in the respective countries at the time when written informed consent is obtained 2. Patients who are able to understand and willing to sign the informed consent form (ICF) 3. Patients who are diagnosed with AML according to the 2016 revision to the World Health Organization classification of myeloid neoplasms and acute leukemia (refer to Appendix 1: WHO Classification of Acute Myeloid Leukemia) 4. Patients who have a sufficient archival or fresh BM aspiration sample for the evaluation of relevant exploratory endpoint. 
Note: Patients who do not have sufficient archival BM aspiration sample and refuse to repeat the procedure may be enrolled in the trial only after written confirmation by ASLAN

5. Patients who are ineligible for standard treatment of AML including but not limited to the following conditions:
 - Newly diagnosed patients who are ineligible for standard therapy namely standard dose induction chemotherapy and reduced dose chemotherapy;
 - Patients who relapsed from prior remission;

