	
Treatment Period: All patients will receive a continuous 28-day treatment cycle of ASLAN003 until disease relapse, treatment failure (defined as failure to achieve a PR or higher within 4 cycles), development of unacceptable toxicity, withdrawal of consent or death.
 
Follow-up Period: All patients will be required to complete a safety follow-up visit within 28 days after the last dose of study treatment. All patients achieving CR or CRi will be followed for survival every 12 weeks post end of treatment (EOT) until disease relapse or death (in the absence of disease relapse) to find out the RFS.
 
The planned duration of entire study (treatment and follow-up) is approximately 2 years.

Study Assessments:
	
The schedule of the assessment for the study is provided in Table 1.
 
Safety Assessments: Patient safety will be evaluated based on the incidence of AEs and serious AEs (SAEs), physical examination, vital signs (blood pressure [systolic and diastolic], heart rate, respiratory rate, weight, and body temperature), ECG parameters, and clinical laboratory tests (hematology, clinical chemistry, coagulation and urinalysis).
 
All AEs will be evaluated according to NCI-CTCAE 4.03 and will be captured from the time of informed consent and continued until the safety follow-up assessment (28 days after last administration of study treatment). For the purpose of this study, fluctuations of pre-existing conditions that do not represent a clinically significant exacerbation or worsening are not to be considered AEs.
 
Pharmacokinetic Assessments (Part 1 ONLY): The blood samples for determination of plasma concentration of study drug will be collected on Day 1 and Day 8 at the following timepoints of Cycle 1 for QD regime: pre-dose, 1, 2, 4, 5, 6, 8, and 24 hours post dose.
 
In BID regime i.e 100mg BID and 200mg BID the PK sampling will be done at following timepoints: pre-dose, 1,2, 4, 5, 6, 8, and 12 hours (or evening pre-dose).
 
The plasma concentration-time data will be used to calculate the PK parameters for ASLAN003 and metabolite.” Part 2: will be determined by SC if needed.

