4.3 Patient Withdrawal and Replacement

Patients may withdraw from any part of the study at any time without penalty and for any reason without prejudice to his or her future medical care. The Investigator will advise the Sponsor of the withdrawal of any patient.

Patients must be withdrawn from study drug under the following circumstances:

- Patient voluntarily withdraws from study participation;
- Disease recurrence;
- Ineffective treatment;
- Unacceptable toxicity;
- Patient's withdrawal of consent;
- Death;
- Pregnancy (refer to section 6.3.1.11)
- Significant protocol deviation;
- Lost to follow-up;
- If deemed by the Investigator that it is not in the patient's interest to continue with the study.

Withdraws from study participation (follow-up permitted):

Patients withdrawing from the study drug will be encouraged where possible to return to the site for a study follow-up visit, in particular for safety evaluations, study assessments and survival follow-up.

Disease recurrence:

Sites should continue to perform efficacy assessments for patients achieving CR or CRi until disease recurrence (or death in the absence of recurrence) in accordance with IWG criteria for AML. Patients will be withdrawn from the treatment if there is evidence of disease recurrence as defined by IWG Criteria¹⁶ (Cheson, 2003).

Ineffective treatment:

The study drug may be discontinued in the event of:

- Treatment failure (in patients who do not achieve a PR or above after 4 cycles of treatment)
- Relapse, as defined by the IWG Response criteria (for patients with a CR or CRi)
- No longer meeting the criteria for a PR (in patients who were previously determined to have a PR)

Once ineffective treatment has been established, as described above, no further efficacy assessments are required.

Unacceptable toxicity:

If the symptoms are not controlled with standard treatments and are considered to be clinically significant, study drug will be stopped and the patient will be withdrawn from the study drug. Patients removed from study drug for unacceptable toxicity will be followed until resolution or stabilization of the AE.

Patients with a response (CR or CRi) withdrawn from the treatment prior to disease relapse should continue to be followed until the relapse in accordance with the study plan.

Consent Withdrawal:

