3.1.1 Overall Complete Remission Rate

Overall complete remission rate (OCRR) is a co-primary endpoint in Part 1 and the primary endpoint in Part 2. It will be derived programmatically from the BM aspiration and peripheral blood results based on the IWG Criteria¹⁶ for AML (Cheson, 2003) as described below.

For patients without sufficient archival BM sample, BM aspiration will be performed during Screening. All patients will receive bone marrow aspiration for efficacy assessment on Day 1 of Cycle 2, 3, 4, 5 and will be repeated every 3 cycles after Cycle 5. Patients who've already achieved CR could omit the bone marrow aspiration at subsequent visits if there is a normal complete blood count with differential of the peripheral blood. Investigator may perform more frequent exam if required based on clinical judgment.

BM aspiration smears will be processed locally.

Following treatment discontinuation, patients who have achieved a CR or CRi, will continue to be followed up for every 12 weeks to assess the relapse free survival. For patients who have not achieved a CR or CRi during treatment, no further follow-up is required following treatment discontinuation.

These criteria categorize the visit response into the following response classifications:

- *CR with incomplete recovery of neutrophils and platelets (CRi):*

Achievement of CRi requires patients to satisfy all of the following:

- A disappearance of blasts in the peripheral blood.
- A decrease in BM blasts to <5% total BM nucleated cells demonstrated in BM aspirate.
- Absence of Auer rods
- No persistent extramedullary leukaemia

- *Complete Remission:*

Patient satisfies all of the criteria above and in addition has:

- Recovery of Neutrophils to $\geq 1.0 \times 10^9/L$ and Platelets to $\geq 100 \times 10^9/L$
- Transfusion-independence

- *Partial Remission:*

A PR is defined as recovery of neutrophils to $\geq 1.0 \times 10^9/L$ and Platelets to $\geq 100 \times 10^9/L$ and either:

- If the pre-treatment bone marrow blast percentage was 50% to 100%, the percentage of blast must decrease to a value between 5% and 25%
- If the pre-treatment BM blast percentage was 20% to less than 49%, they must decrease by at least half to a value of more than 5%

- A reduction in BM blast cells to <5% but with persistence of Auer rods.

- *Treatment failure:*

Failure to meet the criteria for CR, CRi or PR after 4 cycles of treatment will result in a best response of treatment failure.

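### Dose intensity for partial responders stops at cycle 4, although neither document counts partial remission (PR) as treatment failure

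*SAP*

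**What the plan says.** SAP 3.2.2 defines two measures. PID compares the dose given with the dose planned up to treatment failure or relapse. RDI does the same but also stops at treatment discontinuation. For both, patients are split by their status for the overall complete remission rate: CR or CRi is a responder, and "a non-responder will be all other patients (including those with a best response of PR". The plan behind the measures is described as "treatment until relapse (if responding) else for 4 cycles when treatment failure would be declared". A bullet then sets the rule at issue: "For patients with a best response of PR, any dosing data collected after the first 4 cycles will not be taken into account".

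The same section says RDI reflects dosing over the period in which the patient was actually dosed. Its RDI formula ends at the earlier of progression (or a censoring event) and the last day of dosing.

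Other sections describe PR differently:

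- Protocol Synopsis (Study Duration) and 3.4 make treatment continue until, among other events, "treatment failure (defined as failure to achieve a PR or higher within 4 cycles".
- SAP 3.1.1: "Failure to meet the criteria for CR, CRi or PR after 4 cycles of treatment will result in a best response of treatment failure".
- Protocol 4.3 gives partial responders their own ground for ineffective treatment: "No longer meeting the criteria for a PR (in patients who were previously determined to have a PR".
- A footnote to the Synopsis design diagram, attached to the first three Part 1 cohorts, reads: "If showing clinical benefit in the patient, ASLAN003 will be continued until disease progression". The clinical benefit rate counts PR as benefit.

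Dose intensity belongs to the Part 1 primary safety and tolerability endpoint and to the Part 2 secondary one (Protocol 3.3.1 and 3.3.2).

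**The concern.** The 4-cycle cut is justified by an event, declaration of treatment failure, that by definition does not happen to a patient in PR. Nothing in the protocol stops treatment at cycle 4 for such a patient, so dosing in cycle 5 and later is on plan.

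The two neighbouring bullets in SAP 3.2.2 show the mismatch. For CR/CRi and for treatment failure, dosing is dropped only where the investigator carries on past the planned stop. The PR bullet has no such condition and drops planned dosing.

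A programmer also cannot satisfy both the bullet and the description of RDI for a partial responder dosed beyond cycle 4.

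No other planned summary table makes up for the loss:

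- Exposure counts days regardless of dose reductions (SAP 3.2.2).
- By-cycle summaries cover only the first 3 cycles, plus overall (SAP 7.7.1).
- SAP 9.1 lists no table of dose reductions.

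Cohort averages would therefore mix windows: to relapse for CR/CRi, and to cycle 4 for PR.

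**Working it through.** The documents give no PID or RDI value and no expected PR rate or duration. There is no figure to reproduce, and what follows is an illustration.

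**Inputs**

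- RDI = 100% × d/D, with d the dose given and D the dose intended (SAP 3.2.2).
- Cycles of 28 days.
- Daily doses q: 100 mg (100 mg QD), 200 mg (200 mg QD or 100 mg BID) and 400 mg (200 mg BID).
- A reduction step of 50 mg (Protocol 5.3, Table 2). Assumption: this means 50 mg per day, also for BID.
- Assumption: a patient with best response PR takes full dose in cycles 1-4 and 50 mg/day less from cycle 5 to cycle n.

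**Under the SAP bullet.** Only cycles 1-4 count: d = D = 28 × 4 × q, so RDI = 100% whatever n is. PID cut at cycle 4 is also 100%.

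**Over the whole dosing period.** d = 28 × [4q + (n − 4)(q − 50)] and D = 28 × nq, so RDI = 100% × [1 − 50(n − 4)/(nq)].

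For n = 8:

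- 100 mg/day: 1 − 200/800 = 75%
- 200 mg/day: 1 − 200/1600 = 87.5%
- 400 mg/day: 1 − 200/3200 = 93.8%

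| Daily dose | n = 5 | n = 6 | n = 8 | n = 12 | SAP bullet |
|---|---|---|---|---|---|
| 100 mg | 90.0% | 83.3% | 75.0% | 66.7% | 100% |
| 200 mg | 95.0% | 91.7% | 87.5% | 83.3% | 100% |
| 400 mg | 97.5% | 95.8% | 93.8% | 91.7% | 100% |

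If the 50 mg step were per administration under BID (100 mg/day), the n = 8 values would be 1 − 400/1600 = 75% for 100 mg BID and 1 − 400/3200 = 87.5% for 200 mg BID.

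**Effect on a cohort mean, all other patients at 100%**

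- Part 1, one such patient among 6 (n = 8): the mean falls by 25/6 = 4.2 points at 100 mg/day, 12.5/6 = 2.1 at 200 mg/day, or 6.25/6 = 1.0 at 400 mg/day.
- Part 2, 20 patients, those affected at 87.5%: one gives (87.5 + 19 × 100)/20 = 99.4%; five give (5 × 87.5 + 15 × 100)/20 = 96.9%.

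**The opposite direction.** Take 200 mg/day, reduced to 150 mg/day in cycles 3-4 and restored for cycles 5-8. The cut gives (2 × 200 + 2 × 150)/(4 × 200) = 700/800 = 87.5%. The whole period gives (700 + 4 × 200)/1600 = 1500/1600 = 93.8%. Here the bullet makes tolerability look worse. Protocol 5.3 allows return to a higher dose, and Protocol 5.4 allows escalation within a patient.

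**The case against.** The strongest defence is that the late data are not lost. A second swimmer plot shows dose modifications and interruptions (SAP 7.7.1), and Listing 16.2.5.1 gives study drug administration. Late whole-day interruptions still lower actual exposure. With 6 patients per cohort these outputs can be read patient by patient. No test or threshold is attached to PID or RDI, and dose selection looks at the data as a whole (Protocol 6.1 and 8.4.2). All of this stands, and it keeps the point small. It does not make the bullet consistent with the rest of the plan.

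A fixed 4-cycle window can also be defended for PID, because it always gives a denominator. Patients without CR or CRi need no follow-up after discontinuation (Protocol 6.2; SAP 3.1.1). If a partial responder stops early for toxicity, loss of PR is never observed. This stands, and it rules out loss of PR as the only end point for PID. It does not help RDI, which stops at discontinuation anyway.

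Three stronger readings are tempting, and the documents do not support them:

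- **The rule hides late reductions or flatters the drug.** They are absent from PID and RDI only, and restorations and escalations are dropped too, so the direction of error is not fixed.
- **It affects the patients who stay on drug longest.** CR/CRi patients are treated to relapse, and no PR duration is given.
- **It penalises early loss of PR.** If PR is lost and drug stopped at the end of cycle 3 at full dose, a 4-cycle plan gives PID = 3/4 = 75%. But the formula ends the intended dose at progression, and if loss of PR counts as progression, PID = 3/3 = 100%. The bullet excludes dosing after cycle 4; it does not itself set a 4-cycle denominator. The text is ambiguous here, so 75% is one reading only.

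**Conclusion.** The inconsistency is real and minor. SAP 3.2.2 removes planned dosing after cycle 4 for best response PR on a premise that the protocol and SAP 3.1.1 contradict, and it conflicts with its own description of RDI. Dose changes after cycle 4 in these patients, up or down, do not reach the dose-intensity summaries.

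For a late reduction of 50 mg/day, a reported 100% stands for 66.7% to 97.5% over 5 to 12 cycles, depending on dose and duration. This rests on the assumed dosing pattern and on reading the 50 mg step as per day. The effect in the actual trial cannot be stated, because it depends on how many patients have PR as best response and how long they stay on drug. The point concerns the analysis window only and implies nothing about how patients should be dosed.

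**What to change.** In SAP 3.2.2:

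1. **RDI.** For best response PR, count dosing to the earlier of documented loss of PR and last dose.
2. **PID.** State one horizon that can always be computed. An example is the later of the end of cycle 4 and the last dose, ending at documented loss of PR if that is earlier. A patient who stops for toxicity at the end of cycle 3 while still in PR would then have PID 3/4 = 75%; one whose PR is documented as lost at that time would have 100%. With this horizon PID equals RDI for anyone stopping after cycle 4.
3. **Wording.** Align the PR bullet, the responder/non-responder definition, the sentence describing the treatment plan, and the references to progression in both formulas. Keep the 4-cycle limit for best response of treatment failure.
4. **Label.** If a 4-cycle PID is kept for partial responders, call it a first-4-cycles measure.

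The cost is a revision of several sentences in one section and one changed end date per measure. The dosing data are already collected. The SAP also needs a derived loss-of-PR date, since it defines relapse only for CR/CRi responders. That date will be imprecise after cycle 5, when scheduled marrow is taken every 12 weeks, which is three 28-day cycles.

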3.3 Pharmacokinetic Endpoints

Part 1

The PK of ASLAN003 and LAS186558 (active metabolite) will be determined at selected time points. The following PK parameters will be evaluated where possible for ASLAN003:

Cycle 1 Day 1 and Day 8:

- Maximum observed plasma concentration (C_{max})
- C_{max} at steady state ($C_{max ss}$)
- Trough plasma concentration (C_{trough})
- Time corresponding to occurrence of C_{max} (t_{max})
- Time corresponding to occurrence of $C_{max ss}$ ($t_{max ss}$)
- Area Under the Curve from 0 to the time of the last quantifiable concentration (AUC_{last})
- AUC_{last} at steady state ($AUC_{last ss}$)
- Area under the plasma concentration-time curve over the dosing interval (AUC_{tau})
- AUC_{tau} at steady state ($AUC_{tau ss}$)
- Terminal half-life ($t_{1/2}$)
- Effective elimination half-life at steady state ($t_{1/2 eff}$)
- Area Under the Curve from 0 to infinity (AUC_{inf})
- Apparent total clearance of the drug from plasma after oral administration (CL/F)
- Apparent volume of distribution after oral administration (V_z/F)
- Accumulation ratio for AUC ($RacAUC_{tau}$ or $RacAUC_{last}$) (Day 8/Day 1)
- Accumulation ratio for C_{max} ($RacC_{max}$) (Day 8/Day 1)

The following PK parameters will be evaluated where possible for LAS186558 on Cycle 1 Day 1 and Day 8: C_{max} , $C_{max ss}$, C_{trough} , t_{max} , $t_{max ss}$, AUC_{last} , $AUC_{last ss}$, AUC_{tau} , $AUC_{tau ss}$, $t_{1/2}$, $t_{1/2 eff}$, $RacAUC$, $RacC_{max}$, metabolic ratio (MR) for C_{max} (MRC_{max}) and AUC (MRAUC).

Dose-normalized C_{max} , $C_{max ss}$, AUC_{last} , $AUC_{last ss}$, and $AUC_{tau ss}$ parameters will be also calculated for ASLAN003 and its metabolite LAS186558.

